The short-term impact of Botulinum Neurotoxin-A on muscle morphology and gait in children with spastic cerebral palsy

NCT number: NCT05126693

Protocol date: May 10, 2022

Study protocol

This study will include participants of two different projects. Both projects are approved by the local ethics committee of the University Hospitals Leuven, Belgium (s59945 TAMTA project, s62187 and s62645 3D-MMAP project) (Ethische Commissie Onderzoek KU Leuven/UZ Leuven). Written informed consent will be obtained from the parents or legal guardian. Participants will be included between May 2019 and June 2022.

Participants

Children aged between 3-11 years, GMFCS levels I-III with SCP, scheduled for BoNT-A in the MG and/or ST, as part of a multilevel treatment, will be included. Participants will be recruited via two parallel prospective studies. Both studies will investigate the effect of integrated BoNT-A treatment on muscle morphology and gait, while one study will also evaluate the effects on spasticity (s59945 TAMTA project). The selection criteria for the participants are similar in both studies. The exclusion criteria are: any signs of dystonia or ataxia in the lower limbs, severe muscle weakness or poor selectivity in the plantar flexors or knee flexors and cognitive problems that would impede the measurements, intrathecal baclofen pump, previous muscle surgery in the lower limbs or selective dorsal rhizotomy, previous bony corrections in the lower limb within two years before assessments, previous BoNT-A treatment within six months before the baseline assessment or within six months before the pre-BoNT-A 3DGA. Additionally, the physical therapy frequency has to be consistent for at least three months before inclusion. The participants will be measured twice, before and 8-10 weeks after BoNT-A treatment, to evaluate the short-term effects. All children (of both studies) will receive 3DfUS assessments and a 3DGA with clinical examination of the lower limbs. A subset of children (i.e. the participants of one of the two studies) will undergo an additional instrumented spasticity assessment in order to evaluate the BoNT-A-induced tone reduction. During the follow-up, all children will receive usual care including intensive physical therapy, orthotic management, and oral tone reduction if needed.

An age- and functional severity-matched (group-matching based on age and GMFCS level) control group, meeting the same inclusion criteria as the intervention group, but not receiving any intervention apart from their usual care, will be included. The participants of the control group will be recruited via Cerebral Palsy Reference Center of the University Hospitals Leuven, Belgium and the Inkendaal Rehabilitation Hospital Vlezenbeek, Belgium. All children eligible for inclusion will be measured, however the final data selection will be based on accurate matching with the participants in the intervention group. The participants in the control group will undergo 3DfUS measurements only, with an interval of 8-10 weeks between the two assessments.

Procedure

The most affected leg, based on the most recent clinical examination (highest modified Ashworth score for the ankle and knee joints), will be assessed. Measures of body mass, height, total leg length and lower leg length will be taken. A standardized anamnesis will be performed to request treatment history and usual care details.

Muscle selection for BoNT-A injection will be primarily based on the most recent clinical examination and multidisciplinary evaluation of the 3DGA data. BoNT-A, Onabotulinum toxin A (Botox®, Allergan) injections will be applied by a pediatric orthopedic surgeon under general (mask) anesthesia, guided by ultrasonography or palpation. A dose of 100 units of BoNT-A will be diluted in 5ml of saline. The BoNT-A dilution will be injected at multiple sites, in areas with the largest concentration of motor endplates in the muscles selected for treatment. A maximum of 50 units will be injected per site. BoNT-A is suggested to be more effective when part of an integrated approach, i.e., combined with casting, orthotic wear and physical therapy. Therefore, lower leg casts and removable upper leg casts will be applied as indicated.

All additional study assessments (3DfUS, clinical examination, instrumented spasticity assessment and 3DGA) will be performed by three trained assessors. The pre- and post-assessments will always be performed by the same assessor.

Assessments

1. Muscle morphology

Muscle morphology of the MG and distal compartment of the ST muscle will be assessed by 3DfUS. This technique, combining B-mode ultrasonography with three-dimensional motion tracking, is proven valid and reliable in muscle morphology assessments in children with SCP in previous studies.

Ultrasound assessments will be performed while the participant will be placed in prone position. The lower leg will be supported by a triangular cushion to allow slight knee flexion (approximately 25 degrees) and avoid bi-articular stretch on the MG and ST. The ankle will be in resting position without fixation. The joint angles will be measured by goniometry.

Large amounts of acoustic transmission gel will be used to assure smooth movement of the transducer and optimal contact between the transducer and skin. An additional curved gel pad, the Portico, will be used to reduce muscle deformation during the acquisition. Muscle images will be recorded by Stradwin software (version 6.0; Mechanical Engineering, Cambridge University, Cambridge, UK) while moving the transducer from muscle origin to tendinous insertion. The acquisitions will be repeated in case of bad quality images, movement or muscle contraction or when the bony landmarks or muscle borders are missed.

After data collection, the muscle images will be processed by a trained assessor using the Stradwin software (version 6.0; Mechanical Engineering, Cambridge University, Cambridge, UK). Muscle volume (in millimeters) will be estimated by the cubic planimetry technique based on segmentations that will be manually drawn along the inside of the muscle borders in 5-10% of the transverse 2D muscle images. Additionally, echogenicity intensity, as a proxy of muscle quality, will be based on the average of the interpolated reconstruction of the muscle and will be expressed as a gray value on an 8-bit scale (values between 0-255), whereby higher values (whither images) will indicate reduced muscle quality. Muscle belly lengths will be calculated as the Euclidean distance between the muscle origin (MG: posterior surface of medial femoral condyle, ST: ischial tuberosity) and the muscle-tendon junction. The tendon length of the MG will be calculated between the muscle-tendon junction and tendinous insertion. The MTU length of the MG will be calculated by adding the muscle belly to the tendon length.

In order to compare children with different body dimensions, muscle volume will be normalized to the product of body mass*height, and muscle and tendon lengths will be expressed as a percentage of total leg length.

The absolute muscle-specific growth rates for muscle volume during the period between the two assessments will be calculated by the following formulas:

$$\text{growth rate, muscle volume} = \frac{\text{muscle volume (mL) POST} - \text{muscle volume (mL) PRE}}{\text{age (months) POST} - \text{age (months) PRE}}$$

The primary outcomes will include the normalized muscle volume and echogenicity intensity of the MG and distal compartment of the ST and the absolute muscle volume growth rates.

2. Gait analysis

Gait, over ground barefoot walking at a self-selected speed, will be assessed by 3DGA in a 10 to 12 camera (Oxford Metrics, Oxford, UK) gait lab (Vicon Motion Systems, Oxford, UK). Twelve reflective markers will be placed on anatomical landmarks according the Vicon Plug-In-Gait lower limb model. Ground reaction forces will be measured with force plates (Advanced Mechanical Technology Inc., USA) that are embedded in the walkway. During the 3DGA, kinematic data (joint angles for ankle, knee and hip, and segmental orientation of pelvis and foot), kinetic data (joint moments and power) and surface EMG data of the medial gastrocnemius, soleus, tibialis anterior, rectus femoris, vastus lateralis, the medial and lateral hamstrings and gluteus medius will be collected for each leg. The kinematic data of the most affected leg (same as for the 3DfUS and instrumented spasticity assessments) and a selection of spatial-temporal parameters will be included in this current investigation, but the kinetic and EMG data will not be included in any of the analyses.

Gait cycles will be identified and manually marked using the Vicon Nexus software (Oxford Metrics, Oxford, UK). All trials will be exported and imported to a custom-made Matlab script (The MathWorks, Natick, MA, USA, 2020b). All gait cycles will be judged on quality. Trials will be excluded in case of artefacts, gaps in data or indications of inaccurate marker placement. Furthermore, the knee varus-valgus angle will be evaluated and trials with absolute knee varus-valgus ROM exceeding 15 degrees, a knee valgus angle exceeding -10 degrees, or trials that are not representative of the participants' gait pattern will be excluded. As many good-quality steps as possible, will be used to create average trials for the ankle and knee joint kinematics. The GPS, and specific kinematic gait parameters that are found to be sensitive to detect BoNT-A-induced changes, will be extracted per joint. Additionally, the spatial-temporal parameters cadence, walking velocity and stride length will be calculated. Finally the full kinematic waveforms will be exported for pre-post comparison.

The primary outcomes will include the kinematic waveforms, BoNT-A-sensitive kinematic gait parameters, GPS and spatial-temporal parameters.

3. Spasticity assessment

A subset of participants (n=14) will undergo an instrumented spasticity assessment in order to objectively evaluate the change in the hyperactive stretch reflex during passive stretch. This method has been previously described by Bar-On and colleagues and is proven sensitive enough to detect treatment-induced changes.

Four low-velocity (during 5 seconds) passive stretches of the plantar flexors and medial hamstrings will be performed over the full ROM. Next, four full ROM high-velocity passive stretches will be performed whereby the stretch will be performed as fast as possible. The interval between the stretch repetitions will be at least 7 seconds to avoid post-activation depression. During the stretches, muscle activation will be recorded by surface EMG (Zerowire Cometa, Milan, IT)

The raw EMG signals will be filtered by a 6th order zero-phase Butterworth bandpass filter (20-500 Hz) The root mean square envelope of the EMG signal (RMS-EMG) will be computed after application of a low-pass 30 Hz 6th order zero-phase Butter-worth filter.

All data analyses will be carried out with MATLAB Software (The MathWorks, Natick, MA, USA, 2020b). The quality of the individual stretches will be checked using custom-made software. Stretch repetitions will be excluded in case of inconsistent stretch velocities, poor surface EMG data, out-of-plane movement or indications of insufficient participant relaxation (constant EMG activity of the antagonist).

In order to quantify the alteration in muscle tone after BoNT-A treatment, the average RMS-EMG expressed in millivolts, will be calculated as the square root of the area underneath the RMS-EMG time curve, divided by the duration of the time interval, during the high-velocity stretch. The interval will start 200 milliseconds prior to the time point where maximum stretch velocity will be reached and ended at the time corresponding to 90% of the full ROM. This value will be referred to as the muscle activation during a high-velocity stretch. All BoNT-A-induced changes will be compared to previous reported SEM or BoNT-A-induced values.

The average RMS-EMG expressed in millivolts during a high-velocity stretch will be used as the primary outcome to assess alterations in muscle tone. Additionally, the increase during the high-velocity stretch will be calculated by subtracting the muscle activation during a low-velocity stretch, which will be calculated following the same method. This value will be called the change in muscle activation and will be included as a secondary outcome.

4. Clinical examination

A standardized clinical examination including assessments of ROM, spasticity, selectivity and strength will be performed during the pre- and post-BoNT-A assessments of the intervention group and during the pre-assessment of the control group. These data will be used to describe and compare both groups at baseline. The maximal dorsiflexion angle and popliteal angle (unilateral) will be assessed by goniometry. The level of spasticity will be assessed by the modified Ashworth scale and modified Tardieu scale. Muscle strength will be assessed by manual muscle testing, and selectivity will be assessed by the Selective Control Assessment of the Lower Extremity. The evaluations of strength and selectivity will not be included in the current investigation.

5. Statistical Analysis

Normality of data distribution will be checked by a Kolmogorov-Smirnov test ($p < 0.05$). When most parameters are not normally distributed, non-parametric statistical tests will be performed.

Participant characteristics, maximal dorsiflexion angle (measured with the knee extended), popliteal angle (unilateral), and normalized muscle morphology parameters of the intervention and control group will be compared at baseline by a Mann-Whitney U test.

A Wilcoxon signed rank test will be used to evaluate (within) treatment effects in muscle morphology, instrumented spasticity assessment outcomes, spatial-temporal parameters of the 3DGAs ($\alpha = 0.05$). A Bonferroni correction will be applied for the gait kinematic parameters per joint (ankle: $\alpha = 0.05/4 = 0.0125$, knee: $\alpha = 0.05/3 = 0.0167$). Gait parameters will be considered meaningful if statistically significant changes will be noted that are exceeding the SEM or MCID.

Additionally, median difference scores ($x_{\text{post}} - x_{\text{pre}}$) for muscle morphology parameters will be calculated in both the intervention and control group and between-group differences were tested by a Mann Whitney-U test. Additionally, the changes will be expressed as a percentage change of the baseline values for both groups.

Paired t-tests of the ankle and knee kinematics over the entire gait cycle using SnPM analysis will be performed to identify treatment-induced changes in these sagittal plane motions. The averaged ankle and knee kinematic waveforms, consisting of 101 points will be imported to the SPM1d software (version 0.4, available for download at <http://www.spm1d.org/>) in Matlab (The MathWorks, Natick, MA, USA, version 2020b). Clusters will be formed if the critical threshold, based on random field theory, will be crossed ($\alpha = 0.05$). In case of significant clusters, the p-value, details on the location and the duration (percentages of the entire gait cycle) will be reported. Clusters will be considered meaningful when their duration was exceeding 3% of the gait cycle and whether the differences between the means of the pre- and post-BoNT-A joint kinematics will be exceeding the respective SEMs.

References

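### Does the plan need to say which children enter each muscle's test, when BoNT-A may go into the MG, the ST or both?

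*Combined protocol and SAP*

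**What the plan says.** Under Participants, eligibility covers children "scheduled for BoNT-A in the MG and/or ST, as part of a multilevel treatment, will be included". The aim of the two source projects is put more broadly: "Both studies will investigate the effect of integrated BoNT-A treatment on muscle morphology and gait". Assessment is for everyone: "All children (of both studies) will receive 3DfUS assessments and a 3DGA with clinical examination of the lower limbs".

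Under Procedure, the injected muscles are chosen child by child: "Muscle selection for BoNT-A injection will be primarily based on the most recent clinical examination and multidisciplinary evaluation of the 3DGA data". The leg assessed is the more affected one by Ashworth score.

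Section 1 (Muscle morphology) states: "Muscle morphology of the MG and distal compartment of the ST muscle will be assessed by 3DfUS". Both muscles carry primary outcomes: "The primary outcomes will include the normalized muscle volume and echogenicity intensity of the MG and distal compartment of the ST". Section 3 (Spasticity assessment) covers both muscle groups in a subset of 14: "passive stretches of the plantar flexors and medial hamstrings will be performed over the full ROM".

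Section 5 (Statistical Analysis) uses a Wilcoxon signed rank test within the treated group and a Mann-Whitney U test on change scores against controls. It gives no set of children per muscle. For the control group, "the final data selection will be based on accurate matching with the participants in the intervention group"; the matching is on age and GMFCS level, for the group as a whole.

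**The concern.** A child with only the MG injected could also supply an ST measurement, and the reverse. If all treated children enter both tests, injected and un-injected muscles may be mixed. Where un-injected muscle changes less, the estimated change in volume or echogenicity would be too small to describe injected muscle. If only injected children enter, the sets are smaller and the controls were not matched to them.

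The plan does not say which applies, so the choice could in principle be made after the data are seen, on primary outcomes. The same question arises for RMS-EMG of the plantar flexors and medial hamstrings, where 14 children leave little room for subdivision.

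**Working it through.** **What the text supports.** No section defines a set per muscle, but the plan is not silent.

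- Section 5 computes change scores in the intervention group, which Participants defines as all included children. Literally, that means everyone.
- Other wording leans the other way. Procedure directs the injections to the muscles chosen for treatment, Participants describes the spasticity assessment as measuring the fall in tone that BoNT-A causes, and section 5 speaks of treatment effects.
- Participants says every child has ultrasound, and section 1 names the two muscles. Neither says that both muscles are scanned in every child.

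**Size of any understatement.** The plan has no figure to reproduce: it gives no sample size for the main groups, injected share, effect or SD. All inputs below are assumptions for illustration: change of 0.8 SD in injected muscle, u in un-injected muscle, 0 in controls; 30 treated and 30 controls; two-sided 0.05.

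Mean change if everyone is tested = f × 0.8 + (1 − f) × u, so the understatement is (1 − f)(0.8 − u). With 18 of 30 injected, f = 0.60:

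- u = 0: 0.40 × 0.8 = 0.32 SD
- u = 0.4: 0.40 × 0.4 = 0.16 SD
- u = 0.8: 0.40 × 0 = 0

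At f = 1 it is zero whatever u is.

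**Power** (simulation, 20,000 runs per row, normal differences with SD 1), everyone v injected only:

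| Test | u = 0 | u = 0.4 | u = 0.8 |
|---|---|---|---|
| Mann-Whitney, 18 of 30 injected | 0.385 v 0.711 | 0.648 v 0.722 | 0.838 v 0.722 |
| Signed rank, 18 of 30 injected | 0.644 v 0.874 | 0.905 v 0.879 | 0.985 v 0.879 |
| Signed rank, 8 of 14 injected | 0.286 v 0.424 | 0.551 v 0.430 | 0.775 v 0.433 |

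The injected-only values do not truly depend on u; their small differences are simulation error.

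A normal-approximation check at u = 0, f = 0.60, 25 per group agrees in direction.

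- Everyone: the treated-arm variance is 1 + 0.6 × 0.4 × 0.8² = 1.1536, the standard error √[(1 + 1.1536)/25] = 0.2935, and 0.48/0.2935 − 1.96 = −0.32, giving 37.3%.
- Injected only: the standard error is √(1/25 + 1/15) = 0.3266, and 0.8/0.3266 − 1.96 = 0.49, giving 68.8%.

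The better set changes with u, and the documents say nothing about u.

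**Controls.** Children injected in a muscle are selected for involvement of that muscle, so restricting the treated arm might be thought to add confounding. Let d be the baseline difference from controls in injected children, d0 that in un-injected children, and r the correlation of baseline with change. The bias is r × d in the injected-only set and r × [f × d + (1 − f) × d0] in the whole group, so restricting adds (1 − f) × r × (d − d0). With assumed f = 0.90, r = 0.3, d = 0.8, d0 = 0, this is 0.10 × 0.3 × 0.8 = 0.024 SD. The full r × d = 0.24 SD is not the cost of restricting, because most of it is present either way.

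**The case for a change.** The strongest case for a change is that these are primary outcomes, that the two sets answer different questions, and that a sentence would settle which applies. An unstated set leaves a choice open once data are in, and the table shows that it could matter in either direction. Neither the mention of treatment effects nor that of the muscles chosen for injection defines an analysis set.

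The omission stands; the case for changing the plan does not.

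- Nothing in the documents shows that any child had only one muscle injected, so the size may be nil.
- The choice is less stark than a BoNT-A effect against an integrated-treatment effect. Casting as indicated, orthoses and physical therapy accompany the injections, so an injected-only set also estimates integrated treatment, in injected muscle. Calling it the effect of BoNT-A alone would claim too much.
- No set can be shown to be the better primary one from what the plan provides, so a proposed rule would only hand the choice back to the sponsor.
- Running both sets would add morphology tests, for which section 5 states no multiplicity correction, and would split the spasticity subset of 14.

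**Conclusion.** No change follows. The plan leaves out a detail that analysts can fill sensibly: use the muscles that were injected, or the whole treated group as section 5 literally reads, and report the number of children for each muscle. Either is legitimate, and either estimates an effect of integrated treatment.

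The possible understatement is (1 − f) times the difference in change between injected and un-injected muscle. It cannot be sized from the documents and may be zero. The 0.32 SD and the power figures rest wholly on assumed values, and those figures favour different sets under different assumptions, so they show no wrong result.

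This conclusion assumes that the report will name the set behind each MG, ST and RMS-EMG result. If it did not, a reader could not tell whether a result described injected muscle or all treated children; that would be a fault of reporting, not a defect in the design or the tests.

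### No masking is described for the hand-drawn muscle borders, and the non-randomised control comparison of change is unadjusted and may drop measured controls: two separate, cheap improvements

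*Combined protocol and SAP*

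**What the plan says.** **Reading.** Under Assessments, 1. Muscle morphology, volume comes from "segmentations that will be manually drawn along the inside of the muscle borders", in a small share of the transverse images. Echogenicity intensity "will be based on the average of the interpolated reconstruction of the muscle", so it depends on the borders only through the region that is averaged. On who does this: "After data collection, the muscle images will be processed by a trained assessor using the Stradwin software". The Procedure section says that the study assessments, ultrasound included, "will be performed by three trained assessors", with one assessor seeing a child at both visits. That gives consistency, not masking. Masking to group or time point is not described anywhere.

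**Control comparison.** The Participants section describes "group-matching based on age and GMFCS level" and then: "All children eligible for inclusion will be measured, however the final data selection will be based on accurate matching with the participants", meaning the treated children. It gives no tolerance, ratio, target number or procedure, and does not say whether the muscle results are visible when the choice is made. Section 5, Statistical Analysis, compares the groups at baseline by Mann-Whitney, with no stated consequence of an imbalance. It compares post-minus-pre differences in morphology by another Mann-Whitney test with no covariate.

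**What rests on this.** "The primary outcomes will include the normalized muscle volume and echogenicity intensity of the MG and distal compartment of the ST", together with absolute volume growth rates. One size correction is described for volume: "In order to compare children with different body dimensions, muscle volume will be normalized to the product of body mass*height". Growth rate is in mL per month and is not normalised. Section 5 does not explicitly name growth rate in the between-group test.

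**The concern.** The two points have different consequences.

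1. **Reading.** A processor who knows that an image was taken after injection, or belongs to a treated child, can draw borders slightly differently without intending to. That would reach the within-group Wilcoxon tests of morphology and the between-group test of change, mainly for volume.

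2. **Control comparison.** The control group is what separates treatment change from ordinary growth. Allocation is not random, and matching group distributions does not fix which children are kept. If a systematic age or GMFCS difference remains and change depends on it, the unadjusted test attributes it to treatment. Leaving out children who have already been scanned twice also loses information. Only the between-group morphology comparison is exposed.

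Gait and spasticity results are not touched by either point.

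**Working it through.** **Inputs.** The documents give no group sizes, number of controls measured, SD of change or reader error for morphology, so there is no planned figure to reproduce. Everything below uses assumed sizes, two-sided tests at 0.05 and no true effect.

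**Precision.** Let nT children be treated, nC controls measured and nT controls kept, with equal SDs. Then

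SE(kept) / SE(all) = sqrt[(2/nT) / (1/nT + 1/nC)] = sqrt[2nC / (nT + nC)].

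| nT | nC | Dropped | Ratio |
|---|---|---|---|
| 20 | 25 | 5 | sqrt(50/45) = 1.054 |
| 20 | 30 | 10 | sqrt(60/50) = 1.095 |
| 25 | 30 | 5 | sqrt(60/55) = 1.044 |
| 25 | 35 | 10 | sqrt(70/60) = 1.080 |
| 25 | 40 | 15 | sqrt(80/65) = 1.109 |
| 30 | 35 | 5 | sqrt(70/65) = 1.038 |
| 30 | 40 | 10 | sqrt(80/70) = 1.069 |

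The standard error is 4-11% larger. If no control is dropped, the loss is nil.

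**Type I error.** This was simulated with 4,000 runs per setting (3,420-3,995 usable; Monte Carlo SE about 0.35 points at 5%), at (treated, controls) = (20,30), (25,40) and (30,40). Treated ages are uniform over 3-11 and GMFCS I-III equally likely. The control pool is either the same, or older and milder (mean age 7.9 against 7.0; GMFCS 45/33/22%). The age-change correlation is 0, 0.3 or 0.5. The kept subset is the first random draw with Mann-Whitney p>=0.05 on age and on GMFCS level, without use of outcomes. This is a modelling device, not a rule in the plan.

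| Analysis | Same pool | Older, milder pool |
|---|---|---|
| Kept subset, unadjusted | 4.1-5.1% | 4.1-5.7% at correlation 0-0.3; 6.9-7.2% at 0.5 |
| All controls, unadjusted | not needed here | 4.1-4.7% at 0; 6.3-7.0% at 0.3; 8.8-10.2% at 0.5 |
| All controls, ranked change on group, age, GMFCS | 4.7-5.5% | 4.4-5.3% |

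A repeat run put the older-pool figure for the kept subset at correlation 0.5 at about 7-8%. The simulated age effect is linear, which favours the adjusted model.

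In the same pool, the mean absolute age gap was 0.56/0.50/0.46 years under the device and 0.58/0.52/0.48 years with no matching at all; about 90-91% of random draws passed. The signed gap was within 0.02 years of zero. That is chance imbalance, which the test's null distribution already covers, and it is not counted as bias.

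**Reading.** No size is claimed. As a threshold only: a systematic PRE/POST reading shift of 0.159, 0.143 or 0.128 SD of the change score (n = 20, 25, 30) would take the Wilcoxon error rate from 5% to 10%. A shift in treated children only of 0.217, 0.202 or 0.182 SD (same n per group) would do the same for the Mann-Whitney test. Whether shifts of that size occur cannot be told from the documents.

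**The case against.** **Matching is pre-named and does its job.** Age and GMFCS level are fixed in advance and are not outcomes. An outcome-blind choice keeps the error rate near 5% when the pools are alike. In the older pool the matched subset does better than an unadjusted analysis of all controls. All of this stands, and it is why the matched test should stay. The older pool and the 0.5 correlation over 8-10 weeks are assumptions that nothing in the documents supports; controls must meet the same inclusion criteria.

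**Mitigating text.** Normalisation to body size, and the added reporting of change relative to baseline, limit the dependence on size. This also stands, although the relative change has no test attached and neither adjusts for age or GMFCS level. Growth rate escapes normalisation, but that matters here only if it enters the between-group test, which Section 5 does not say.

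**Stronger readings that the documents do not support.**
- A reader might infer that controls are picked to suit the result. Taking the lowest p-value among 3 to 10 admissible subsets would give 8-17% type I error, but that is hypothetical misuse and nothing in the text suggests it. The plan is silent on the safeguard, no more.
- A reader might take the baseline Mann-Whitney comparison as the selection rule. Section 5 only compares the groups.
- A reader might infer that the processor is one of the scanners and knows the group. The shared job description does not show this; the plan simply does not separate the roles.
- That no masking is described does not show that reads were unmasked.

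**Conclusion.** Both points hold as cheap improvements, not as demonstrated bias.

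The reading point concerns a primary outcome and reaches both the within-group and between-group tests, mainly for volume. Its size cannot be estimated from the documents.

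The control point is narrower. Residual systematic age or GMFCS differences are not corrected, and dropped controls cost 4-11% in standard error under the assumed sizes. Inflation to about 7-8% needs both an older, milder control pool and an age-change correlation of 0.5; otherwise the matched, unadjusted test stays close to 5%. If every measured control is kept, only the lack of adjustment remains.

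**What to change.** 1. **Reading.** Give image files random codes so that the existing processor segments without seeing group or time point, at least for all images not yet processed. Report any images read unmasked.
2. **Analysis.** Add a pre-specified between-group analysis of change adjusted for age and GMFCS level (for example, regression of ranked change), using all measured eligible controls. Report it beside the matched Mann-Whitney test. Name the outcomes it covers, growth rate included or not, and fix in advance which of the two analyses is primary.
3. **Selection.** Choose the matched set from age and GMFCS level only, to a written tolerance, without access to muscle results. Report how many controls were measured and how many were left out.

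**Cost.** Plan wording, a short selection routine and a coding list held by someone already on the team.

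**Downsides.** The adjusted analysis needs a modelling assumption for the age effect. A close match makes the unadjusted test conservative if age matters: 2.3-3.1% in the same-pool simulation at correlation 0.5, taking the closest of 200 random subsets. Masking may be only partial, because the protocol is dated May 2022, inclusion runs to June 2022, and some images may already have been processed.
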